
Participants will be recruited via flyers and social media posting. Those who are interested in participating in the study will tell the researchers if they are interested in participating in the research study or will reach out via email. We will explain the purpose of the study, as well as study procedures to the potential participant. We will also provide copies of the written consent document and confirm that participants meet the inclusion criteria during this initial exchange. During this initial exchange, we will verify that the potential participant has met each of the inclusion criterion, listed on the flyer. If the participants need further clarity, or have more questions, we will provide them with a phone number for them to call us so we can answer their questions with more detail. If the potential participant expresses continued interest in enrolling in the study, we will schedule a time for them to come to the Clinical Research Laboratory (CRL) on the Syracuse University campus (Women's Building Room 303) so that we may guide them through the written consent document and begin the consent process.

If participants are interested and eligible, they will be instructed via email (1-2 days prior to actual visit days) to wear comfortable, normal, everyday athletic wear for their in-person visits. Participants will be asked to come to the SUNY Upstate Clinical Research Unit followed by SU Clinical Research Laboratory Visit after an overnight fast of 10-12 hours.

B) Pre-Intervention Lab Visits:

All data are collected following standardized procedures and by the same investigators at all timepoints to minimize potential errors of measurements. All participants will provide written informed consent prior to study involvement in accordance with university institutional review board guidelines. The following outlines the specific measurements that will be taken and the specific protocol for lab visit one.

(a) SUNY Upstate Visit (Clinical Research Unit):

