After 10- to 12-hr of overnight fasting, participants will come to SUNY Upstate (Clinical Research Unit; Institute For Human Performance Rm# 1223) to undergo their 2-hour oral glucose tolerance test (OGTT) with multiple blood draws (venous blood samples will be obtained at -15, 0, 30, 60, 90 and 120 min), directed by [name] (a director of Clinical Research Unit) and/or registered nurses ([name], CCRC). At time 0 min, participants will drink a standard 75 g glucose solution purchased commercially. Youth will be administered 1.75 g glucose per kg (not to exceed 75 g). After the last blood sample ($t = 120$ min), participants will be provided a snack and allowed for the Syracuse University Visit.

Note that [name], a director of Clinical Research Unit, upon [name] agreement, will submit a separate IRB application to the SUNY Upstate Medical School.

(b) Syracuse University Visit (Clinical Research Lab & Human Performance Lab):

- After the SUNY Upstate Visit (at the Clinical Research Lab at SU), participants' standing height and weight will be assessed without shoes, wearing light clothing, to the nearest 0.1 cm using a stadiometer and balance beam scale to the nearest 0.1 kg, respectively. Body composition and visceral fat will be estimated by multi-frequency bioelectrical impedance (BIA) InBody (Inbody 770, South Korea). For the InBody assessment, participants stand barefoot on the platform of the device with the soles of their feet on the electrodes. They then grasp the handles of the unit with their thumb and fingers to maintain direct contact with the electrodes and remain still for ~1 min while keeping their elbows fully extended and their shoulder joint abducted to around 30° angle (Figure 1).

- We will measure waist and hip circumferences. Participants will stand straight with their arms out while a tape measure is wrapped around their waist and hip. Measurements will be taken to the nearest cm.

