- Participants' lipid profile will be collected by Cholestech Analyzer using a blood sample obtained via a finger stick (Figure 2). Participants will select which finger they wish to use, then the researcher (wearing gloves) will clean the fingertip with an alcohol swap. Then, the researcher will "stick" the finger to draw blood. The first drop of blood will be wiped away, and the second drop will be collected and used for analysis. This may cause slight discomfort but is relatively quick and painless. After this the researcher will provide a clean gauze, to clean the area, and a band-aid (if needed).

- We will gain parameters related to cardiovascular function by using a blood pressure monitor. Participants will be asked to sit quietly for five minutes with minimal movement. After this we will place the cuff on their right upper arm (bicep area) and start the measurement. The cuff will inflate, deflate, and then reinflate again. We will ask participants not to move during this process. All of the equipment will be disinfected prior to distribution with disposable wipes (antiviral/antibacterial/antifungal) by a researcher wearing gloves before and after every time collection is performed on a participant.

- We escort participants across the hall (less than 10 feet) to the Human Performance Lab where we will take the following pre-clinical marker (Carotid-femoral pulse wave velocity [PWV]) of CVD. Participants will be escorted to a padded exam table. They will lie down and rest for approximately 5 minutes. Blood pressure in the upper arm will be measured using an automated device with a cuff that wraps around the upper arm and inflates and deflates, applying pressure to the arm. Next, we will obtain blood pressure in the wrist (radial artery), neck (carotid artery), and upper leg (femoral artery) using an applanation tonometer (SphygmoCor, AtCor Medical). This technique is non-invasive, requiring approximately 5 minutes for completion. A picture of the technique is attached. A tonometer is a very sensitive force transducer (similar in appearance to a watch battery affixed to a pen). This pen is placed over the artery of interest providing an accurate recording of the blood pressure wave. With each pulsation of the arterial pulse, a force is generated against the tonometer. The tonometer records this force wave

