(b) High Intensity Interval Training (HIIT) trial: The 4-week HIIT intervention will use a stationary bicycle performed 3 times/week (a total of 12 sessions over the 4-week), performing at the CRL. All participants will perform a 20-minute HIIT protocol (20 repetitions of 10-seconds work time followed by 50-seconds resting/active recovery for the first two weeks, and 10 repetitions of 20-seconds work time followed by 100-seconds resting/active recovery for the rest of two weeks; targeted 90% HR_{max}) after 5-minute warm-up (10% HR_{max}). The supervisor (PI: [name] and/or Graduate researcher: [name]) will provide encouragement and supervision for exercise adherence. Heart rate (Polar, Polar Electro Oy, Kempele, Finland) and rating of perceived exertion (RPE; detail described in the questionnaire section) will be recorded.

(c) Control group: Participants randomized into the control group will be told to maintain their daily lifestyle and dietary habits for the duration of the four weeks.

D) Post-Intervention Lab Visits:

Following completion of the 4-week intervention, individuals will be asked to come back to undergo same screening/measurements of the Pre-Intervention Lab Visit (SUNY Upstate and Syracuse University visits). An email will be sent to participants on their last day of the intervention with available time and dates for their visit. This will ensure all individuals will be tested with a similar fasting schedule, regardless of what group they were in.

4.2. Describe how you will have sufficient time to conduct and complete the research?

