The anticipated time for each visit (Pre- and Post- Intervention Visits) will take approximately 5-6 hours including our measurements performed and transportation between SU and SUNY Upstate. PI ([name] [name]) and graduate researchers ([name], [name], [name]) haven already been involved in similar projects so that team members can split hours or days to secure successful completion of the study (performing study procedure and supervising participants during the intervention) in time. This study is designed to be completed in one year. We do not anticipate any issues around time constraints for completing this study. [name] has generally 2+2 teaching load with minimal service dedication thereby securing his time commitment to the research. [name] is a director of Clinical Research Unit at SUNY update and agreed (as a scientific consultant) that we will have all participants being underwent OGTTs at the cite (i.e., research/service cost: ~\$150, covered by [name] startup funds) will be paid to the Research Unit).

4.3. Surveys, interviews, questionnaires will be conducted:

No (Skip to 4.4)
 Yes Include all research instruments including surveys, questionnaires, sample interview questions, etc. as separate appendices. If the survey instrument is commonly used in your discipline, only provide a citation to the instrument.

4.4. Community Based Participatory Research (CBPR) is described as research that is conducted as an equal partnership between traditionally trained "experts" and members of a community. Is this research categorized as CBPR?

No. (Skip to 4.5)
 Yes. Please explain: _____
4.4.1. In CBPR research studies, the community participates fully in all aspects of the research process including conception, design, and analysis.
With this in mind, describe how you plan to engage community members in your research study:

4.4.2. Describe how you plan to provide community members with appropriate training for human subjects research? Include in your description what training will be provided.

4.4.3. Describe your plan to disseminate research findings with members of the community throughout the course of your study.

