The study design was developed over a series of in-person meetings; roles and responsibilities for all research personnel have been explicitly identified, as well as a timeline of activities. [name] has been informed of the protocol and specific research-related duties and functions and will be supervised by [name] [name] throughout all phases of the study. Prior to enrolling participants, we will hold regular lab meetings (weekly emails, Zoom meetings) to review specific roles.

6.5. Explain why you do not need additional qualified staff, other than those listed in Sections 1 and 6, to conduct your study.

[name], [name], [name], and [name] will be fully responsible for the primary study. Given its simplicity of data collection procedure, consent form, anthropometric and blood draw, will be collected by these four investigators.

7. Characteristics of Participants

7.1. Approximate Number of Participants to be recruited: 50

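### The team that supervises the intervention also measures waist, hip and pulse wave velocity, and the protocol neither separates the two roles nor masks the assessor

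*Protocol*

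**What the plan says.** **The rule for measurement.** Section 4.1 B calls for standard procedures and has all data gathered "by the same investigators at all timepoints to minimize potential errors of measurements". The reason given is consistency of measurement. Section 4.1 D repeats the same measurements after the intervention.

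**Who supervises.** Under section 4.1 C(b), the PI and/or a graduate researcher oversees the HIIT sessions (3 per week for 4 weeks, 12 in total) and "will provide encouragement and supervision for exercise adherence".

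**Who does both.** Section 4.2 describes the PI and three graduate researchers as one pool whose work covers "performing study procedure and supervising participants during the intervention", and says that "team members can split hours or days to secure successful completion of the study". Section 6.5 makes four people responsible for the study and explains why no others are needed; among the items it lists, "anthropometric and blood draw, will be collected by these four investigators".

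**The hand-measured outcomes.** Section 4.1 B(b): "We will measure waist and hip circumferences", by tape and to the nearest centimetre. PWV comes from a hand-held tonometer: "This pen is placed over the artery of interest providing an accurate recording of the blood pressure wave".

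**When the group becomes known.** Section 4.1 C places randomisation after the pre-intervention visit is complete.

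The protocol shown nowhere mentions masking, blinding or an assessor separate from the people who deliver the intervention.

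**The concern.** Using the same operator before and after removes differences between operators from the change score. It does nothing about an operator who knows the group and expects a certain result. Tape placement and tension, and the choice of an acceptable tonometer waveform, both leave room for judgement. The protocol also records an expectation: section 3.1 cites evidence that TRE reduces waist circumference.

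Baseline is necessarily taken without knowledge of the group, and follow-up is not. A shift tied to group knowledge therefore does not cancel between visits. Randomisation, the separate randomisation by age group and adjustment for baseline all leave it in the between-group difference. Nor can it be repaired at the analysis stage, because the data do not show which part of a reading is expectation. This is a matter of trial conduct, to be settled before the readings are taken.

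**Working it through.** **Step 1. Who can measure whom.**

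| Question | Where | Answer |
|---|---|---|
| Who measures? | 4.1 B, 6.5 | Same investigators throughout; four people for anthropometry |
| Who supervises HIIT? | 4.1 C(b) | PI and/or a graduate researcher |
| Are the two pools distinct? | 4.2 | No; one team covers both |
| Is the group hidden from the assessor? | Nowhere | No provision |
| Is baseline before allocation? | 4.1 C | Yes |

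The overlap is established for the team. It cannot be established person by person, because names are removed from the text.

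**Step 2. Which outcomes are exposed.** Waist, hip and PWV depend on the operator's hand. The other main measurements are less exposed: the glucose tolerance test is run by the other site's staff (4.1 B(a), 12.2), lipids come from an analyser, body composition from InBody, and blood pressure from a cuff monitor (described as automated before tonometry).

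**Step 3. How a shift enters the comparison.** Let *b* be the difference between groups in the mean follow-up reading that is due only to knowledge of the group, in SDs of the change score. Baseline carries no such term, so with no true effect the expected difference in change is *b* − 0 = *b*.

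**Step 4. Illustrative size.** The protocol gives no SD, effect size or error rate for these outcomes, so there is no figure of its own to reproduce. Inputs from the protocol (4.1): 20 TRE, 20 HIIT, 10 control. Assumed: *b*, a two-sided 5% t-test, no dropout, and a variance pooled over three groups (50 − 3 = 47 df).

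SE in SD units = √(1/n₁ + 1/n₂):
- active arm vs control: √(1/20 + 1/10) = 0.387
- TRE vs HIIT: √(1/20 + 1/20) = 0.316

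The false-positive rate is P(|T| > 2.012), where T is non-central t with 47 df and non-centrality *b*/SE.

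| *b* (assumed) | Active vs control: *b*/SE | Error | TRE vs HIIT: *b*/SE | Error |
|---|---|---|---|---|
| 0 | 0 | 5.0% | 0 | 5.0% |
| 0.1 | 0.26 | 5.7% | 0.32 | 6.1% |
| 0.2 | 0.52 | 8.0% | 0.63 | 9.5% |
| 0.4 | 1.03 | 17.3% | 1.26 | 23.6% |

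With two-group degrees of freedom (28 and 38), the rates at 0.2 SD are 7.9% and 9.5%, and at 0.4 SD 17.0% and 23.4%. The choice of df hardly matters.

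**Step 5. Reading the two pairs of columns.** They are separate scenarios. If assessors favour both active arms equally over control, *b* for TRE vs HIIT is zero and that error stays at 5%. The TRE vs HIIT rates apply only if assessors favour one active arm over the other.

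**Step 6. Can the existing team do it?** At most two roles (the PI and a graduate researcher) are named for HIIT supervision. If the four people of section 6.5 are the PI and three graduate researchers of section 4.2, at least 4 − 2 = 2 remain who need not supervise HIIT. The load is 20 × 12 = 240 HIIT sessions and 50 × 2 = 100 measurement visits, of which 50 follow randomisation.

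**The case against.** **The same-operator rule is sound, and nothing in it obliges a supervisor to measure.** This stands. The rule should stay; the gap is that the protocol has no second safeguard beside it.

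**Overlap of persons is not shown.** A reader might infer that the HIIT supervisor does take the outcomes of the participants he or she coached. The documents do not support that. Splitting hours or days is compatible with different people doing the two jobs, section 6.5 mentions anthropometry but not PWV, and the PWV laboratory has its own manager (5.1). What stands is that the protocol permits the overlap and hides no group from any assessor.

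**Supervised sessions are described for HIIT only.** TRE is home-based and controls have no sessions, so the coaching link concerns one arm. Knowledge of the group at follow-up is possible in all three.

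**The trial's main inference may not rest on these outcomes.** A reader might extend the point to every outcome, including blood pressure. Step 2 shows why that goes too far. The protocol shown also does not identify a hand-measured outcome as primary.

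**Handling by study ID is already planned.** Correct: sections 11.2, 11.4 and 11.5 provide for it in data sheets, acquisition software and stored samples, so nothing needs adding there. It does not mask the person holding the tape or the tonometer.

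**The bias sizes are invented.** They are assumptions, and the protocol offers nothing to replace them. They show sensitivity and do not estimate a bias.

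**Masking is not free.** Section 11.2 gives much of the team access to the spreadsheets, section 11.5 has weekly meetings on progress, and HIIT is held in the laboratory where waist and hip are measured. This stands and is counted in the cost.

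**Conclusion.** The point holds in a limited form. For waist, hip and PWV, the protocol lets a person who supervised a participant take the follow-up reading knowing the group, and its one stated safeguard does not address that. Any resulting shift enters the change score in full.

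The size is unknown. Under an assumed bias of 0.2 to 0.4 SD in one active arm against control, a nominal 5% error becomes about 8% to 17%. The corresponding 9.5% to 24% for TRE vs HIIT needs the further assumption that one active arm is favoured over the other, although section 3.1 says it is unknown which will do better. These rates are not evidence that results will be biased. The documents support neither a claim of actual person-level overlap nor one that the whole trial is compromised. This is an inexpensive improvement that should be made before follow-up visits are rostered.

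**What to change.** Keep the same-operator sentence in section 4.1 B and add, for waist, hip and PWV only:

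- For each participant, the readings at both visits are taken by one listed team member who does not supervise that participant's exercise sessions or diet.
- As far as feasible, that assessor is not told the group until the post-intervention readings are recorded.
- Participants are asked not to disclose their group to the assessor.
- Until then, allocation is kept out of the spreadsheets the assessor can open and out of meeting discussion the assessor attends.

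Sections 4.2, 11.2 and 11.5 need matching wording. On the assumption in step 6 of the working, no new staff are needed; sample size and measurement procedures do not change. The costs are less flexible rostering across 100 visits, some restriction on data access and weekly meetings, and masking that will fail when a participant reveals the group or is seen training in the shared laboratory. Separating the roles still helps when masking fails, because the assessor will not have coached that participant.

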7.4.2. Explain the rationale for using this particular group(s): _____

7.5. List all study specific inclusion/eligibility criteria (e.g.-gender, age range, population characteristics, location, etc.):

A) Adolescents (age 14-17 years old with sex- and race-specific BMI percentile $\geq 85^{\text{th}}$) and young adults with overweight and obesity (age 18 to 30 years old with BMI $\geq 25 \text{ kg/m}^2$)

B) Free from the following chronic medical conditions: heart disease, arrhythmias, diabetes, thyroid disease, bleeding disorder, history of pulmonary disease, hypertension, hepatorenal disease, musculoskeletal disorder, neuromuscular/neurological disease, autoimmune disease, cancer, peptic ulcers, anemia, or chronic infection (HIV).

C) Have not taken any heart, pulmonary, thyroid, anti-hyperlipidemic, hypoglycemic, anti- hypertensive, endocrinologic (e.g., thyroid, insulin, etc.), emotional/psychotropic (e.g., Prednisone, Ritalin, Adderall), neuromuscular/neurological, or androgenic medications (anabolic steroids).

D) Live in the greater Syracuse area.

E) Does not have a pacemaker.

F) For females: are not pregnant or lactating.

We will explain details of the health conditions for the participants to make sure they understand each health condition completely. We will also examine their body composition before we determine whether they are qualified to participate in the study. During the study, if participants have concerns regarding their health conditions, they are free to refuse to participate, or to withdraw from the study at any time. If there is concern about their medical safety, we may recommend participants seek medical attention. During the initial visit, physicians are not being consulted.

Inclusion criteria will be monitored by [name] [name] and [name], when they contact him and communicate about the study procedure via email and/or phone (i.e., potential eligible participants screened by the initial email/phone contact will be determined).

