The reason we are looking at individuals with overweight and obesity exclusively (Inclusion A), is because we are targeting individuals at high risk for cardiometabolic diseases, such as type 2 diabetes and cardiovascular disease with the purpose of disease prevention. The reason for inclusion criteria B-D is those factors have been shown to impact weight, and therefore could be potential confounders. Due to the two required visits to the lab (i.e., pre- and post- intervention), we need participants who are local (Inclusion E). Since we will be measuring body composition with a BIA device, these individuals will not be able to partake (Inclusion F).

7.6. List all study specific the exclusion/ineligibility criteria. The exclusion criteria must parallel the inclusion criteria:

- A) Adolescents (age <14 years old and/or sex- and race-specific BMI percentile <85th) and adults with normal weight or overweight adults (Age >30 years old and/or BMI <25 kg/m²) will be excluded in the study.
- B) Have at least one of the following chronic medical conditions: heart disease, arrhythmias, diabetes, thyroid disease, bleeding disorder, history of pulmonary disease, hypertension, hepatorenal disease, musculoskeletal disorder, neuromuscular/neurological disease, autoimmune disease, cancer, peptic ulcers, anemia, or chronic infection (HIV).
- C) Have taken any of the following medications: heart, pulmonary, thyroid, anti-hyperlipidemic, hypoglycemic, anti- hypertensive, endocrinologic (e.g., thyroid, insulin, etc.), emotional/psychotropic (e.g., Prednisone, Ritalin, Adderall), neuromuscular/neurological, or androgenic medications (anabolic steroids).
- D) Does not live in the greater Syracuse area.
- E) Has a pacemaker.
- F) For females: are not pregnant or lactating.

We will explain details of the health conditions for the participants to make sure they understand each health condition completely. We will also examine their body composition and blood glucose before we determine whether they are qualified to participate in the study. During the study, if participants have concerns regarding their health conditions, they are free to refuse to participate, or to withdraw from the study at any time. If there is concern about their medical safety, we may recommend participants seek medical attention.

Exclusion criteria will be monitored by [name] [name] and [name], when they contact him and communicate about the study procedure via email and/or phone.

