7.7. Does this research involve participants likely to be vulnerable to coercion or undue influence?

- No. (Skip to 7.8)**
- Yes. If yes, describe the additional protections included in the protocol to protect their rights and welfare.**

7.8. General state of Health: ("Unknown" - unless you will obtain health data on participants prior to beginning the study.)

As we indicated in the inclusion criteria, this study will recruit adolescents (age 14-17 years old with sex- and race-specific BMI percentile $\geq 85^{\text{th}}$) and young adults with overweight and obesity (age 18 to 30 years old with BMI $\geq 25 \text{ kg/m}^2$). Therefore, general state of health of all participants will be weight status (normal weight, overweight, obese) determined by age and BMI obtained prior to beginning the study (when we check participants' eligibility).

8. Recruitment of Participants

8.1. Describe in detail how participants will be identified and recruited. Include in your description how you will have access to a population that will allow recruitment for the number of participants required for your research. Do not merely state "Volunteers".

The study population will consist of individuals recruited from Syracuse University, other local colleges/universities as well as individuals in the local communities. Participants will be recruited via paper flyers and social media postings. Flyers will also be attached to departmental research boards around the Syracuse campus. If participants are interested in our study after seeing the flyer, they will contact us at the e-mail provided in the flyer. If participants are interested in the study after seeing the social media (CRL and HPL official Instagram accounts) post, they will contact us at the e-mail provided in the post. The flyers will be used for the social media post. The script for recruitment is as follows:

“Dear (name),

My name is [name], and I am a doctoral student in the department of Exercise Science at Syracuse University. I am emailing you regarding your potential interest in our research study.

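### The Methods measure height, weight and body composition only after the fasted OGTT, the recruitment script before it, so an error in reported BMI may surface only after six blood draws

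*Protocol*

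**What the plan says.** All references are to the protocol.

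- **Section 4.1 A (Pre-lab Contacts).** Inclusion criteria are confirmed in the first exchange, which section 7.5 describes as email or phone. For those still interested, "we will schedule a time for them to come to the Clinical Research Laboratory (CRL) on the Syracuse University campus", the purpose being to "guide them through the written consent document and begin the consent process". For the fasting day the order is: "Participants will be asked to come to the SUNY Upstate Clinical Research Unit followed by SU Clinical Research Laboratory Visit after an overnight fast".
- **Section 4.1 B(a).** The OGTT takes venous samples at -15, 0, 30, 60, 90 and 120 minutes. The youth glucose load is set per kilogram, capped at 75 g.
- **Section 4.1 B(b).** "After the SUNY Upstate Visit (at the Clinical Research Lab at SU), participants' standing height and weight will be assessed without shoes". The InBody assessment takes place at the same stop.
- **Section 4.1 C.** Randomization follows completion of the whole pre-intervention visit.
- **Section 7.5.** "We will also examine their body composition before we determine whether they are qualified to participate in the study". Section 7.6 repeats this and adds blood glucose. The rationale after the 7.5 list refers to visits as follows: "Due to the two required visits to the lab (i.e., pre- and post- intervention".
- **Section 7.8.** Weight status is "determined by age and BMI obtained prior to beginning the study (when we check participants' eligibility".
- **Section 8.1 (recruitment script).** Candidates are told that height, weight and body composition are taken at the Clinical Research Lab (CRL) first, and that they are then taken to SUNY Upstate for the OGTT.
- **Section 9.6.** No study procedure starts before written consent.

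**The concern.** BMI, or BMI percentile for ages 14-17, defines the trial population. It can be checked in minutes with a stadiometer and a scale. Under the Methods, the first measured value comes only after the most burdensome part of the baseline day: an overnight fast, a glucose load and repeated venous sampling. Sections 7.5 and 7.6 say that an in-person measurement feeds the decision on qualification, so the remote check is not the final word. Section 7.8 reads as if BMI were already settled by then, and the script tells candidates that the order is the other way round.

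At stake are unnecessary procedures in people, some of them minors, who turn out not to qualify, and an eligibility decision whose data source is not defined.

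**Working it through.** The protocol gives no figure to reproduce. The check is a comparison of sequences, with a little arithmetic on size.

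**Step 1. Sequence in each source**

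| Step | Section 4.1 (Methods) | Section 8.1 (script) |
|---|---|---|
| Remote screen, reported BMI | first | first contact by email or phone |
| Consent appointment at the CRL | after the remote screen, under pre-lab contacts | consent form attached to the email; no separate appointment mentioned |
| OGTT at SUNY Upstate | before measurement | after measurement |
| Measured height, weight, body composition | after the OGTT | before the OGTT |
| Randomization | after the whole visit | not placed relative to the visit |

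The two columns disagree on the order of OGTT and measurement. Sections 7.5 and 7.6 (body composition examined before qualification is decided), read with section 4.1 B, put the final decision after the OGTT. Read with section 8.1, they put the measurement before it. Section 7.8 does not say whether its BMI is reported or measured.

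**Step 2. Exposure of one late screen failure**

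- Venous draws: -15, 0, 30, 60, 90, 120 min = 6.
- Direct cost: about $150 for the OGTT (section 4.2, read as per test), plus $10 for an incomplete visit or $50 for a completed one (sections 8.4.1 and 8.4.2). That is $150 + $10 = $160 to $150 + $50 = $200.
- Time: up to most of a visit of 5-6 hours (section 4.2).

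**Step 3. How small an error crosses the adult cut-off**

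BMI = weight / height². At 72.25 kg and 1.70 m: 72.25 / 2.8900 = 25.0. At 1.72 m: 72.25 / 2.9584 = 24.4. At 1.68 m: 72.25 / 2.8224 = 25.6.

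Suppose an adult reports 1.70 m, is really taller by d, and reports weight correctly. The person looks eligible but is not if reported BMI lies between 25.0 and 25 × ((1.70 + d) / 1.70)². The values of d are my assumptions, since the protocol gives no reporting error:

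| d | Upper end of the misclassified band |
|---|---|
| 1 cm | 25 × 2.9241 / 2.8900 = 25.3 |
| 2 cm | 25 × 2.9584 / 2.8900 = 25.6 |
| 3 cm | 25 × 2.9929 / 2.8900 = 25.9 |

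The documents do not allow an estimate of how many of the 50 participants would fall in such a band, or a similar calculation for the adolescent percentile criterion.

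**Step 4. A related dependency**

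The per-kilogram youth load needs a body weight at the OGTT, but section 4.1 B measures weight only afterwards. The cap applies from 75 / 1.75 = 42.9 kg upwards, so the gap matters only below that weight.

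**The case against.** **Eligibility is checked before the visit.** Sections 4.1 A, 7.5 and 7.8 all place a check at first contact. This stands: BMI eligibility is not first considered after the OGTT. What comes late is its measured confirmation.

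**The measurement could be made at the consent appointment.** Section 5.1 places the InBody in the CRL, and the candidate is there for consent. The protocol does not exclude this, but nowhere says it. The fix amounts to saying it.

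**The OGTT may itself be a screening step.** Section 7.6 lists blood glucose among the items examined before qualification. If that glucose comes from the OGTT, some later exclusions are intended and an earlier BMI check will not remove them. This stands, but it gives no reason to leave a non-invasive check of height and weight until after the blood draws.

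**Stronger readings a reader might infer, which the documents do not support:**

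- *Consent may follow the OGTT.* The consent appointment stands under pre-lab contacts, section 4.1 B requires written consent before involvement, and section 9.6 allows no procedure without it. No text puts consent after the OGTT.
- *The visit count makes the plan impossible.* The two visits are the pre- and post-intervention assessments. They cannot be all attendances, since the HIIT arm comes to the CRL for 3 × 4 = 12 sessions. A separate consent appointment is compatible with that count, though it is not spelled out.
- *Normal-weight people will be enrolled, or the comparison will be biased.* Under either order measured BMI is available before randomization (section 4.1 C). Enrolment would require staff to disregard a measured value, and nothing in the documents suggests that. Section 4.1 C names no BMI check at that step, which is a reason to state one, not evidence of bias.

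**Conclusion.** The point holds in a limited form. Section 4.1 and the recruitment script contradict each other on whether height, weight and body composition come before or after the OGTT, and the protocol does not say whether reported or measured BMI decides eligibility. Under the Methods order, a volunteer whose reported BMI is wrong can complete the fast, glucose load and six draws before being found ineligible, at about $160 to $200 in direct cost and up to most of a 5-6 hour visit.

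The number affected is unknown. The bands in the working rest on assumed height errors of 1 to 3 cm at a reported height of 1.70 m, and on the OGTT fee being per test. The consequence is avoidable burden and an unclear eligibility source. Neither the between-group comparison nor the timing of consent is impugned. The change is worth making because it is cheap.

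**What to change.** 1. In section 4.1 A, make the CRL appointment a consent and screening step. After signed consent (parental consent plus assent for minors), measure height and weight on the existing stadiometer and scale, and confirm BMI or percentile eligibility before booking the OGTT.
2. State that measured BMI decides eligibility and that the email or phone check is a pre-screen. Align sections 7.5, 7.6 and 7.8 with this, and say which blood glucose section 7.6 means.
3. Keep outcome weight and body composition at the pre-intervention visit, so that the baseline data are unchanged.
4. Give one site order in sections 4.1 and 8.1, and say in section 7.5 and the script that the consent appointment is additional to the two assessment visits.
5. Reconcile, within section 4.1 B, the per-kilogram youth glucose load with a body weight that is measured only later that day.

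The cost is protocol and script wording plus a few minutes at an appointment already described, with equipment already on site. The downside is that candidates must be told of that short campus visit. The change does not prevent exclusions based on OGTT glucose, and it does not recover volunteers wrongly turned away on a reported BMI below the cut-off.
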